#### **4.2.2 Secondary objectives**

For the **secondary objectives 3 and 4**, Speech intelligibility (SI) in quiet will be assessed with the Freiburger monosyllabic speech test where the outcome measure is percent correctly repeated words. The hypotheses related to the third and fourth objectives are:

**H0 (Objective 3)** SI(study HA) is not significantly different from SI without HAs

**H1(Objective 3)** SI(study HA) is significantly better than SI without HAs

**H0 (Objective 4)** SI(study HA) is significantly worse than SI(own HAs).

**H1(Objective 4)** There is no difference between SI(study HA) and SI(own HAs)

A significant difference means that the study HAs are inferior to own HAs, otherwise they are non-inferior.

The **secondary objective 5** will be assessed by calculating the absolute differences between the NAL-NL2 Target curves (Keidser et al 2011) realised in the Otometrics/Natus Freefit and the measured REAR/REIG curves after First Fit and after Fine-Tuning, if applicable. The expectation is that the deviation from the target curves is  $\leq$  5dB in the frequency range 0.25-4 kHz

The **secondary objective 6** will be addressed by asking the participants to rate speech understanding, localization and quality of sound in different situations as well as listening effort after having worn the hearing aids 10-14 days in real-life on a scale from 0-10 with a shortform of the SSQ questionnaire (SSQ 17 German Version, Kiessling 2011) in different situations. Mean rating will be calculated across the participants for each HA. For each domain we will test whether the ratings are significantly worse with study HAs compared to own HAs, if they are, that indicates the study hearing aids are inferior to own HAs. Otherwise, they are non-inferior.

The **secondary objective 7** will be addressed by asking the participants to rate hearing aid outcomes after having worn the hearing aids 10-14 days in real-life on a 5-point scale with IOI-HA (Cox & Alexander 2002, German Version Cox et al 2002). Mean rating will be calculated across the participants for each HA. For each question we will test whether the ratings are significantly worse with study HAs compared to own HAs, if they are, that indicates the study hearing aids are inferior to own HAs. Otherwise, they are non-inferior.

For the **secondary objective 8**, to evaluate satisfaction, subjects are asked to rate their satisfaction with the hearing aids regarding several aspects including sound, conversations and overall satisfaction after having worn the hearing aids 10-14 days in real-life. In Marke-Trak10 survey (Picou, 2020), respondents rated their satisfaction on a 7-point scale, where 1 indicates very dissatisfied, 4 indicates neutral, and 7 indicates very satisfied. Respondents who indicated scores of 5, 6, or 7 were considered to be satisfied and satisfaction was reported as % satisfied of the study sample. In a similar manner the percentage of satisfied subjects will be calculated for the study HAs and compared to published values of (MarkeTrak10 (Picou, 2020) and EuroTrak German (2022 ), EuroTrak France (2022), EuroTrak Spain (2023) ). For each question we will test whether the proportion of satisfied subjects is significantly lower with study HAs compared to the published values (MarkeTrak/EuroTrak), if they are, that

indicates the study hearing aids are inferior the hearing aids reported on in the MarkeTrak/EuroTrak Reports. Otherwise, they are non-inferior.

In addition, mean ratings will be calculated across the participants and will be compared for the study HAs and own HAs and for each question we will test whether the ratings are significantly worse with study HAs compared to own HAs, if they are, that indicates the study hearing aids are inferior to own HAs. Otherwise, they are non-inferior.

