### **1.4 Overall synopsis of the clinical investigation**

This study will investigate speech understanding, spatial reception and satisfaction with a current hearing aid of WSA as part of the PMCF Process.

The main objective of the study is to investigate if speech understanding with the WSA Hearing Aid (HA) is better than without a hearing aid and not inferior to speech understanding with the participants' own hearing aids.

The study uses a direct approach where n = 20 adult test subjects, all being experienced hearing-aid users with mild-to-moderate sensorineural hearing loss, will be fitted with test hearing aids.

The subjects will complete a test battery in the lab and an assessment in real life with the test hearing aids and their own hearing aids. The study protocol includes two visits to the lab (of duration up to two hours) and a home trial with a duration of 10-14 days. Objective speech tests performed in the lab provide measures of speech intelligibility in quiet and in noise. Subjective self-assessment performed in real-life are done by use of questionnaires where self-perceived performance of the test hearing aid and the subjects' own hearing aid is rated within the main domains of speech intelligibility, listening effort and sound quality. In addition in-situ measurements will be performed to assess the quality of WSAUD fitting to a clinical target (NAL NL2). All these measurements are described in the PMCF

umbrella approval of the Hörzentrum Oldenburg gGmbH at the medical ethics committee (Oldenburg University, Votum 2022-033). Statistical analysis of both speech-test outcomes and self-assessment ratings will be done to test the overall main hypothesis that the test hearing aid offers improved speech understanding over the unaided condition and non-inferior speech understanding and performance ratings compared to the subjects' own hearing aids.

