## **7.2 Statistical analysis**

**Objectives 1 and 2** (Speech in Noise OLSA): The SRT data will be analyzed using a one-tailed paired t-test.

**Objectives 3 and 4** (Speech in Quiet Freiburger): Similarly to the OLSA Test the % correct data will be analyzed using a one-tailed paired t-test.

**Objective 5** (NAL-NL2 Targets): No statistical analysis will be performed, only descriptive statistics will be used.

**Objectives 6-7** (Questionnaires – SSQ17, IOI-HA)

Subjective rating data from real-life questionnaires will be analyzed using one-tailed paired t-tests, comparing ratings of study HA and own HA with a significance level of 0.05 to determine significance.

In addition, descriptive statistics of the SSQ 17 scores and IOI-HA scores will be reported by Hearing Aid (study or own) for each subscale and put into perspective of published data (von Gahlenz et al, 2018; Cox et al, 2013).

**Objective 8** (Questionnaire – Satisfaction)

One-sided test of proportions will be done to analyze whether the proportion of satisfied hearing aid users is significantly lower with study hearing aids than reported in the literature (MarkeTrak 10, EuroTrak). A significant effect indicates that the study hearing aids are inferior, otherwise they are non-inferior.

In addition, subjective rating data from satisfaction questionnaire will be analyzed using one-tailed paired t-tests, comparing ratings of study HA and own HA with a significance level of 0.05.

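### Objectives 6–8 turn every SSQ17 domain and every IOI-HA and Satisfaction question into its own device-level verdict, with no key score or rule for conflicts, so the conclusion on performance ratings is indeterminate

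*Combined protocol and SAP*

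**What the plan says.** Section 4.2.2 sets the unit of testing.

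- SSQ17 (objective 6): "For each domain we will test whether the ratings are significantly worse with study HAs compared to own HAs".
- IOI-HA (objective 7): "For each question we will test whether the ratings are significantly worse with study HAs compared to own HAs".
- Satisfaction (objective 8): "for each question we will test whether the ratings are significantly worse with study HAs compared to own HAs". Each question is also tested for whether the proportion satisfied falls below the values published in MarkeTrak 10 and three EuroTrak reports.

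After each of these the section gives the same two-way rule. A significant result means the study HAs are inferior (to own HAs, or to the HAs in the surveys); anything else means they are non-inferior. The label is attached to the hearing aid, not to the domain or question.

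Section 7.2 gives the methods. For objectives 6–7, "Subjective rating data from real-life questionnaires will be analyzed using one-tailed paired t-tests"; each sets study against own HAs at the 0.05 level. For objective 8, "One-sided test of proportions will be done to analyze whether the proportion of satisfied hearing aid users is significantly lower" than in the literature; no alpha is given for that test. In addition, "subjective rating data from satisfaction questionnaire will be analyzed using one-tailed paired t-tests", again at 0.05.

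Section 1.4 makes the ratings part of the overall main hypothesis: the test device "offers improved speech understanding over the unaided condition and non-inferior speech understanding and performance ratings" relative to own HAs. Neither 4.2.2 nor 7.2 names a leading score, an order of testing, an adjustment for the number of tests, or a rule for combining results.

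**The concern.** Each test gives a verdict on the whole device, and there are many tests. If one IOI-HA question is significant and the others are not, the plan read literally declares the same device inferior once and non-inferior several times. Nothing tells the reader which statement answers the ratings part of the section 1.4 hypothesis. The conclusion in the post-market report would then depend on which items are quoted. Separately, each added 5% test raises the chance that a device equal to the subjects' own is labelled inferior somewhere by chance.

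**Working it through.** **The plan's own figure.** The plan states no error rate across objectives 6–8. Its only stated calculation (section 7.1) is for objective 1: dz 0.77, alpha 0.05, power 0.8, n = 16, and power 0.9 at N = 20. Exact noncentral-t power for a two-sided 0.05 paired test gives 0.821 at n = 16 and 0.904 at n = 20, so those figures reproduce. They say nothing about the questionnaires. Only n = 20 is used below, with n = 16 as a check.

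**Conflicting labels.** This part needs no arithmetic. With m tests, each ending in a statement about the device, the labels agree only if all m tests are significant or none is. Every other outcome gives both labels.

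**Number of tests.**

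- SSQ17: 4.2.2 names speech understanding, localization and sound quality, plus listening effort. That is 4 if effort is its own domain.
- Satisfaction: 4.2.2 names at least 3 aspects, each tested twice (own HAs, published values): 3 × 2 = 6.
- IOI-HA: the number of questions k is not given; assumed 4 to 8.
- Total: 4 + 6 = 10 before any IOI-HA question, and 14 to 18 with k = 4 to 8.
- Own-HA comparisons alone: 4 + 3 + k = 11 to 15.
- If each question is tested against all four published sources separately: 4 + 3 + 12 + k = 23 to 27.

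**Chance of at least one false inferior label, independent tests.** The formula is 1 − 0.95^m.

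- m = 10: 40.1%
- m = 14: 51.2%
- m = 17: 58.2%
- m = 18: 60.3%

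**Correlated items.** Items rated by the same people are probably positively correlated. The table comes from 20,000 simulated data sets per cell, with n = 20 paired differences, a common inter-item correlation r, no true difference, and one-sided t-tests at 0.05.

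| m | independent | r = 0.3 | r = 0.5 | r = 0.7 |
|---|---|---|---|---|
| 10 | 40% | 31% | 25% | 19% |
| 14 | 51% | 38% | 30% | 22% |
| 17 | 58% | 42% | 33% | 23% |

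Results at n = 16 are within about 1 point. At r = 0.9 the figures are 12–13% for m = 10 to 17.

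**Proportion tests.** The simulation treats these as 5% tests, which is an approximation. At n = 20, for assumed reference rates of 0.6 to 0.9, the actual level is 2.1–4.8% (exact binomial) or 4.1–8.7% (z-test). For these tests, equal means equal to the published rate, not to own HAs.

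**Would adjusting alpha be enough?** Bonferroni at m = 14 uses 0.05/14 = 0.0036 per test and brings the overall rate to about 4.9%. But the plan reads non-significance as non-inferior. For a device truly worse by dz = 0.5 at n = 20, power per test falls from 0.70 to 0.25, so a false non-inferior label on that test rises from 30% to 75%.

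**What a summary score does.** The SD of a k-item mean relative to one item is √((1 + (k − 1)r)/k). For an illustrative k = 7 this is 0.63, 0.76 and 0.86 at r = 0.3, 0.5 and 0.7, so a shift common to all items is estimated more precisely. A deficit on one item only shrinks to 1/7 = 0.14 of its size, which is more than the SD shrinks.

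**The case against.** The strongest reply is that these are secondary objectives. Section 4.1 makes only the OLSA comparisons primary, and section 12 limits publications to descriptive statistics. The 0.05 level is stated per comparison; no 5% rate across the set is promised. The error also works against the sponsor's own device and cannot by itself create a false claim of non-inferiority. Domain-level testing suits objective 6, which names several aspects of hearing. And if every item had to pass a margin-based test, false non-inferiority would be controlled without adjustment, at a cost in power.

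Much of this stands. It limits the seriousness of the point and explains why 5% can serve here only as the per-test level. It does not remove the contradiction: section 1.4 puts the ratings in the main hypothesis, section 12 says the data are mainly for the post-market report, and the plan contains neither a margin nor a requirement that every item pass.

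A reader might infer that an equal device is more likely than not to be called inferior. The documents do not support that. Exceeding 50% takes 14 or more nearly independent tests, or about 30 at r = 0.3 (55% at 31 tests). Nor can the seven rated aspects in section 3.1 be taken as the Satisfaction question count: that sentence covers all the questionnaires together and includes localization, which 4.2.2 assigns to SSQ17.

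**Conclusion.** The point holds. Separate unadjusted tests, a device-level label from each, and no rule for conflicts are all in the text, so the ratings part of the section 1.4 hypothesis has no determinate answer. This does not depend on any assumed count.

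The size does. For a truly equal device the chance of at least one false inferior label is roughly 20–60% for about 10–18 tests with inter-item correlation from 0.7 down to 0. It is lower (about 12–13%) only if items are almost interchangeable, and higher if the four published sources are tested separately. The IOI-HA and Satisfaction counts, the common correlation and the 5% level for the proportion tests are assumptions.

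The point leaves the primary OLSA comparisons untouched. Reading non-significance as non-inferior with no margin is a separate and larger weakness in the same sentences; the remedy has to deal with both. The change should be made, but it is not a reason to doubt the study as a whole.

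**What to change.** In sections 4.2.2 and 7.2, name one verdict-bearing score per questionnaire for the comparison of study HAs with own HAs: for example the SSQ17 overall mean, the mean of the IOI-HA items and the overall-satisfaction item. Judge each by the confidence interval of the paired difference against a margin fixed and justified in advance. State what combination of the three supports the ratings part of the section 1.4 hypothesis; if all three must succeed, no adjustment is needed for false non-inferiority. Report domains, single questions and the MarkeTrak/EuroTrak comparisons descriptively, with confidence intervals and without device-level labels.

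Do not lay a fixed testing order over the present hypotheses. Here the favourable result is a non-significant one, so for an equal device the sequence would stop at the first questionnaire 95% of the time. An order makes sense only once the hypotheses are margin-based.

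The cost is rewording plus the work of justifying three margins; no new data or visits are needed. Single items lose a formal verdict, and a deficit confined to one domain is diluted in the summary, so the domain-level intervals must still be shown.

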### **Secondary objectives**

Objective 3: Investigate whether speech intelligibility in quiet is better with the study HAs than without HAs as measured by the German Freiburger test.

Objective 4: Investigate whether speech intelligibility in quiet with the study HAs is non-inferior (i.e. the same or better) compared to speech intelligibility in quiet with the subjects' own HAs as measured by the German Freiburger test.

Objective 5: Investigate how close the study hearing aids fitted with the fitting software to NAL-NL2 Targets match the postulated targets, as measured in-situ with real-ear measurements.

Objective 6: Investigate speech perception, sound localisation, satisfaction and quality of hearing perceived in real-life with the study hearing aids compared to the subjects' own hearing aids as measured by the SSQ17 questionnaire (German version)

Objective 7: Investigate outcomes and effectiveness of hearing aid usage in real-life with the study hearing aids compared to the subjects' own hearing aids as measured by the IOI-HA questionnaire (German version)

Objective 8: Investigate satisfaction in real-life with the study hearing aids compared to the subjects' own hearing aids as measured with the Satisfaction questionnaire (WSA internal questionnaire)

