#### **Inclusion criteria:**

- The allowed audiometric range for HIL is shown below:

- They should be experienced hearing aid users
- Air-Bone-Gap should be less or equal to 20 dB HL.
- Sensorineural HV, mild-to-moderate
- HV corresponding to the fitting range of the HA
- Healthy (outer) ear
- Older than 18 years
- German is mother tongue
- Able to understand the instructions
- Willing to participate in laboratory tests and to wear the HAs at home for 2 weeks
- Informed consent

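### Objective 8: % satisfied is calculated for the study HAs only and labelled against four survey values, so that label moves with who was recruited; the own-HA figure that would calibrate it is collected but not planned

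*Combined protocol and SAP*

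**What the plan says.** **Objective (4.1, Secondary objectives, Objective 8).** The aim is to "Investigate satisfaction in real-life with the study hearing aids compared to the subjects' own hearing aids as measured with the Satisfaction questionnaire". No survey appears as comparator in the objective.

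**Two analyses (4.2.2 and 7.2).**

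- *Proportion satisfied.* On the 7-point scale, scores of 5, 6 or 7 count as satisfied. Section 4.2.2 states that "the percentage of satisfied subjects will be calculated for the study HAs and compared to published values" from MarkeTrak 10 and EuroTrak Germany, France and Spain, and continues: "For each question we will test whether the proportion of satisfied subjects is significantly lower with study HAs compared to the published values". A significant result labels the study HAs inferior to the aids in those reports; anything else is labelled non-inferior. Section 7.2 repeats this: "One-sided test of proportions will be done to analyze whether the proportion of satisfied hearing aid users is significantly lower".
- *Mean ratings.* Section 4.2.2 adds that "mean ratings will be calculated across the participants and will be compared for the study HAs and own HAs", question by question, with a separate inferior/non-inferior reading. Section 7.2 specifies one-tailed paired t-tests at 0.05.

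**Data collected (6.3, Workflow).** The Satisfaction questionnaire is completed after the study-HA home trial and again after the own-HA home trial.

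**Sample (6.1, 6.2).** The plan is for 20 experienced users with mild-to-moderate sensorineural loss, for whom "German is mother tongue" is an inclusion criterion. Limited mobility, limited dexterity and known psychological problems are exclusions. The study HAs are fine-tuned individually and rated after 10-14 days.

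**The concern.** A one-sample test of % satisfied against a fixed published value cannot tell two explanations apart: the device satisfies more or fewer people than the surveyed aids do, or the people recruited are more or less easily satisfied than the survey respondents. Sections 4.2.2 and 7.2 describe no matching or adjustment to the survey populations. The obvious calibration is the same subjects' % satisfied with their own HAs. It could be computed from data already collected, but no section plans it.

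The plan also does not say how four survey comparisons per question are to be read together, or how they relate to the paired rating comparison if the two disagree. What is at stake is a formal label for each satisfaction question in a post-market report, which could be earned or lost through recruitment alone.

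**Working it through.** **Plan's own figure.** Section 7.1 sizes the trial on Objective 1 only (n = 16, recruiting 20). No sample size, margin or power is given for Objective 8, so there is no figure to reproduce here.

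**Inputs.**

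- n = 20 (6.1).
- One-sided test (7.2). The sentence on the test of proportions states no significance level; 0.05 is assumed, as in the neighbouring sentence on ratings.
- Exact binomial test: assumed, since 7.2 does not name the version.
- Survey value p0: not in the documents. Assumed range 0.70 to 0.85.
- Base satisfaction p of this sample with hearing aids: assumed range 0.60 to 0.90.

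**Step 1. Cut-off for 'inferior'.** With X the number satisfied, the label is given if X ≤ c, where c is the largest k with P(X ≤ k | 20, p0) ≤ 0.05.

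| p0 | c | P(X ≤ c), p = p0 |
|---|---|---|
| 0.70 | 10 | 0.048 |
| 0.75 | 11 | 0.041 |
| 0.80 | 12 | 0.032 |
| 0.85 | 13 | 0.022 |

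**Step 2. Same device, different recruits.** Let the study HA be identical to the own HAs, so that both satisfy a proportion p of this sample. With p0 = 0.80, P('inferior') = P(X ≤ 12 | 20, p):

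| p | P('inferior') |
|---|---|
| 0.60 | 0.584 |
| 0.70 | 0.228 |
| 0.80 | 0.032 |
| 0.90 | 0.0004 |

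The device difference is zero in every row; only the sample changes.

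**Step 3. Sensitivity to the version of the test.** With a normal approximation at p0 = 0.80, X = 13 gives z = (0.65 − 0.80)/√(0.80 × 0.20/20) = −0.15/0.0894 = −1.68, below −1.645, so the cut-off becomes 13. The four probabilities become 0.750, 0.392, 0.087 and 0.002. The dependence on recruitment is just as marked.

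**Step 4. Several survey values.** If the published values spanned 0.70 to 0.85, the cut-offs would run from 10 to 13. Counts of 11, 12 or 13 of 20 would then be 'inferior' against the highest value and 'non-inferior' against the lowest. P(11 ≤ X ≤ 13) is 0.344 at a true 70% and 0.505 at a true 60%.

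**Step 5. Within-subject comparison.** Take an exact one-sided McNemar test at n = 20 with no device difference and an assumed 10% of subjects discordant in each direction. It declares 'inferior' with probability 0.009. That probability depends on the discordance and not on how the sample's base rate compares with any survey, so the recruitment effect drops out.

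**The case against.** **The own-HA comparison is in the plan.** A reader might infer that the survey test replaces the comparison Objective 8 asks for. The documents do not support that. Sections 4.2.2 and 7.2 both add a paired comparison of satisfaction ratings, study against own HAs, on the full scale and with its own verdict. This objection stands in full. The point is confined to the % satisfied analysis and its label.

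**The survey label speaks only about the surveyed aids.** Section 4.2.2 words it that way. A reader might infer that a study HA worse than the own HAs would be declared non-inferior to them by this route; the label makes no such claim. Differing labels against different surveys likewise answer different questions and do not contradict each other. Both remarks stand. What remains is that the label credits or blames the device for a difference that the sample alone can produce, and that no rule says how four labels are to be read.

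**A missed deficit is not evidence of confounding.** If 90% were satisfied with own HAs and 70% with the study HAs, the survey test at p0 = 0.80 would still say 'non-inferior' with probability 0.77. It is tempting to blame the survey benchmark for this. But an exact McNemar test on the same 90%/70% case (assumed discordance 25% and 5%) declares 'inferior' only 31% of the time and so misses 69%. Most of the 0.77 reflects n = 20 and the absence of a margin.

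**The inputs are assumed, and the stakes are modest.** No survey percentage is in the documents, so the size is illustrative; the direction does not depend on the values chosen. This is one of two analyses of the last secondary objective, and section 12 says that only descriptive statistics are presented. That limits the weight of the point. It also means that a descriptive survey comparison would fit the plan's own publication policy.

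**Conclusion.** The point holds in limited form. Objective 8 has a matching within-subject analysis of mean ratings. The % satisfied analysis, however, is planned for the study HAs only and labelled against four unadjusted published values, without the own-HA figure that would show how this sample compares with the surveys.

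Under the stated assumptions (n = 20, exact one-sided 0.05, p0 = 0.80), the chance that a device identical to the own HAs is labelled 'inferior' runs from 0.58 to 0.0004 as base satisfaction goes from 0.60 to 0.90. If the survey values spanned 0.70 to 0.85, counts of 11 to 13 of 20 would be labelled differently against different surveys. The documents supply neither the survey values nor the sample's base rate, so these figures show how far the label can move; they do not predict the result.

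The documents give no ground for choosing one survey as the deciding benchmark, and none is proposed here.

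**What to change.** In 4.2.2 and 7.2:

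1. Calculate % satisfied (scores 5-7) for the own HAs exactly as for the study HAs.
2. Report the within-subject difference in % satisfied with a confidence interval, alongside the planned paired comparison of mean ratings.
3. Show study-HA and own-HA % satisfied side by side against each published value, so that the reader can see how far the sample itself departs from each survey.
4. Treat the survey values as descriptive context and draw no inferior/non-inferior label from them.

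**Cost.** Changes of wording in two sections and one extra table from data already collected. The sponsor gives up a formal verdict against market surveys.

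**What it does not solve.** The paired interval will be wide. With the 25%/5% discordance used above, the standard error is √((0.30 − 0.20²)/20) = 0.114, so an approximate 95% interval is ±1.96 × 0.114, about ±22 percentage points. The home-trial order also stays fixed (study HAs first, own HAs second, per 6.3; only the speech-test order is randomised, per 9.4), so an order effect remains mixed with the device difference. Nor does the change make a non-significant result proof of non-inferiority, which is why an interval is asked for and not another label.
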